1.0 Objectives

Primary Objective

To assess the safety of fludarabine and busulfan as a preparative regimen for allogeneic stem cell transplantation in patients with myelofibrosis as determined by non-relapse mortality.

Secondary Objective

To evaluate efficacy of this therapy as determined by:

- 1.1 Engraftment
- 1.2 Complete clinical/hematological remission
- 1.3 Progression free survival
- 1.4 Overall survival

2.0 Background

2.1. Overview of the myeloproliferative disorders:

The myeloproliferative disorders (MPD) are chronic hematological malignancies originating at the level of pluripotent hematopoietic stem cells (1,2). The Philadelphia chromosome negative MPDs classified on the basis of the predominant feature include:

- a) Polycythemia vera (PV): overproduction of red cells
- b) Essential thrombocythemia (ET): overproduction of platelets
- c) Idiopathic Myelofibrosis (IM): bone marrow fibrosis

The concepts common to these disorders are:

- 1) Clonal hematopoiesis
- 2) Transformation to acute leukemia (AL): Up to 10% of PV & ET patients develop AL.
- 3) Progression to myelofibrosis: Up to 10% of patients with ET and PV progress to myelofibrosis with development of massive hepatosplenomegaly, cytopenias and transfusion dependency. Typically, AL occurs following progression to myelofibrosis, although de novo AL is seen. These patients who have progressed to myelofibrosis and/or to acute leukemia have a poor prognosis.

2.2. Idiopathic Myelofibrosis:

Idiopathic myelofibrosis (IM) (agnogenic myeloid metaplasia, myelofibrosis with myeloid metaplasia) is a clonal myeloproliferative disorder due to an acquired somatic mutation of a hematopoietic progenitor cell, resulting in clonal erythrocytes, platelets, granulocytes, monocytes and their precursors. These malignant megakaryocytes and monocytes secrete fibrogenic cytokines – TGF, PDGF, FGF, which cause polyclonal fibroblast proliferation, collagen and reticulin deposition, and eventual bone marrow

fibrosis, the hallmark of the disease. This process progresses to bone marrow failure and extramedullary hematopoiesis (1,3,4).

The annual incidence of IM ranges from 0.5 –1.5 per 100,000, while the median age at diagnosis is 55-65 years. Most patients with IM present with anemia, marked splenomegaly, early satiety and constitutional symptoms. During the clinical course, most experience progressive anemia requiring frequent blood transfusions, and death occurs eventually due to bone marrow failure or leukemic transformation. Current treatment of IM is palliative, consisting of supportive care with blood transfusions, splenectomy (5), splenic radiation, hydroxyurea, and more recently thalidomide (6-9). None of these therapies alter the natural history of this disease.

The median survival is 5 years from diagnosis, but varies from 2 years to greater than 10 years depending on presence or absence of well-defined prognostic indicators. These include anemia (Hb<10gm/dl), advanced age (>64), constitutional symptoms (fever, night sweats, weight loss), leukocytosis (>30,000/l) or leucopenia (<4,000/l), circulating blasts (>1%), and high-risk cytogenetic abnormalities (+8, 12p-). A simple but widely accepted scoring system using two of these factors, namely Hb<10gm/dl and WBC >30,000/l or <4,000/l separates patients into three groups with low (0 factor), intermediate (1 factor), and high (2 factors) risks, associated with a median survival of 93, 26, and 13 months (4,10,11). **We propose to treat patients with intermediate and high-risk disease in this study of allogeneic stem cell transplantation.**

2.3. Allogeneic stem cell transplantation:

Allogeneic hematopoietic cell transplantation by eradicating the malignant clone and restoring normal hematopoiesis would be expected to alter the natural history of IM.

Table 1: Allogeneic transplantation for myelofibrosis.

Study	N	Median Age	NRM	Median Follow up	OS
Guardiola et al (12)	55	42	27%	36 months	47%
Daly et al (13)	25	48	48%	35 months	41%
Deeg et al (14)	56	43	32%	34 months	58%
Rondelli et al (15)*	21	54	10%	31 months	85%
Kroger et al (16)*	21	53	16%	22 months	84%

* Retrospective multicenter studies using multiple reduced intensity regimens

Due to the uncommon occurrence of this disease and older age at disease onset, only five studies with more than 20 patients have been reported in the literature, and all but one are multicenter/registry studies (12-16). In the largest study from the Fred Hutchinson Cancer Center in Seattle, 56 patients with a median age of 43 years were transplanted from HLA-matched donors for myelofibrosis. At the median follow up of 34 months, five-year survival was 58% with continuing resolution of fibrosis, reduction in spleen size, transfusion independence, and improvement in blood counts. Six patients rejected the graft (n=3) or were mixed chimera (n=3). The major reason for treatment failure was transplant related mortality of 32% (14).

A special problem area is the treatment of older or debilitated patients. Guardiola published a series of 55 patients demonstrating inferior results for older patients: Five year survival of 14% in patients older than 45 years compared to the 5 year survival of 62% in younger patients (12). These inferior results in older patients and patients with comorbidity who comprise majority of patients with this disease make myeloablative transplantation a promising but not suitable therapy most patients with myelofibrosis.

Another approach would be to use a reduced intensity or a nonmyeloablative conditioning regimen, which have been reported to extend allogeneic transplant to older patients and patients with other co-morbid medical conditions. Others and we have shown that reduced intensity stem cell transplantation can be safely utilized in older patients and those with comorbidities in other hematological malignancies (17-22). Rondelli et al and Kroger et al have reported encouraging data in multi institutional studies of reduced intensity transplantation in older patients with myelofibrosis as detailed in the table 1(15,16). In these retrospective studies with a median age of 54 years, a non-relapse mortality of 10%-16% and 3 year overall survival of 84%-85% was reported. We wish to prospectively evaluate the role of allogeneic stem cell transplantation using reduced intensity conditioning regimen of fludarabine and busulfan.

2.4 Busulfan and Fludarabine Conditioning

Several reduced intensity regimens have been studied in patients with hematological malignancies (17-22), but it is not clear if one is superior to the other. In this study we

would like to use fludarabine and busulfan as we have studied these agents extensively in myeloid malignancies. Kroger et all used this regimen in a retrospective study in patients with myelofibrosis with 16% non relapse mortality and 84% overall survival (16). In patients with CML, this regimen has been reported to be well tolerated with no treatment related mortality within first 100 days and 85% 5 year disease free survival (23).

3.0 Patient Eligibility

Inclusion Criteria

1. Patients with Idiopathic Myelofibrosis or Myelofibrosis secondary to Polycythemia Vera or Essential Thrombocythemia or Myelodysplastic syndrome with or without fibrosis.
2. Patients 75 years or younger
3. Patients must have an HLA matched or at least a 9/10 antigen (A, B, C, DQ or DR) matched related or unrelated donor.
4. Patients must have a Zubrod PS ≤ 2 .
5. Creatinine < 1.6 mg/dl
6. Ejection fraction $\geq 40\%$, unless cleared by cardiology
7. Serum direct bilirubin < 2 mg/dl (unless due to Gilbert's syndrome), SGPT $\leq 4 \times$ normal values.
8. FEV1, FVC, or DLCO $\geq 40\%$ of expected.
9. Negative Beta HCG test in a woman with child bearing potential defined as not post-menopausal for 12 months or no previous surgical sterilization)

Exclusion Criteria

1. Uncontrolled life-threatening infections
2. HIV positive
3. Patients with active viral hepatitis

4.0 Pretreatment evaluation

Patient :

The following evaluation includes standard test performed to determine patient eligibility and should not be repeated prior to starting treatment unless treatment is delayed for more than 30 days after registration.

- a) Patient medical history and physical examination.
- b) CBC, differential and platelet count
- c) Bone marrow aspiration and biopsy
- d) Chemistry panel
- e) Serology for CMV, HBV, HCV and HIV
- f) B-HCG in women of child bearing potential
- g) Sample to store pre-transplant DNA for future analysis of chimerism

- h) Cardiac ejection fraction
- i) Pulmonary function tests with DLCO
- j) Chest x Ray
- i) Urine analysis

Donor:

Acceptability of the allogeneic stem cell donor (bone marrow or peripheral blood progenitor cell) will be determined according to MDACC Apheresis Unit (for related donors) or National Marrow Donor Program (for unrelated donors) standard operating procedures

5.0 Treatment Plan

5.1 Preparative Regimen

Treatment will start on D-7 as per the schema shown below:

-7	-6	-5	-4	-3	-2	-1	0
		Flu	Flu	Flu	Flu		
Bu test dose 32 mg/m ²	Rest	Bu	Bu	Bu	Bu		
				ATG*	ATG*	ATG*	
							HSCT

Fludarabine 40mg/m²/day IV over 60 mins x 4 days (days -5,-4,-3, and -2)

Busulfan (days -5,-4,-3, and -2)

Rabbit ATG (Thymoglobulin) 2.5 mg/kg (infused over 6 hours) X 3 days (day -3,-2 and -1)*

*Patients with HLA-identical sibling donors do not receive Thymoglobulin.

Donor bone marrow or blood stem cells to be infused on day 0.

BUSULFAN is administered at the dose of 100 mg/m² in normal saline over three (3) hours i.v. every twenty-four (24) hours for four (4) consecutive days (days -5 to -2). The busulfan dose on day -5 to -2 will be altered on the basis of the pharmacokinetic studies to target an AUC of 4000 mMol-min ± 12%. This altered dose will be administered in an identical fashion to the 100 mg/m² dose. If the patients cannot undergo the pharmacokinetic studies, the patient will not receive the 32 mg busulfan "test dose" and will receive the 100 mg/m² dose day -5 to -2. Patients may also undergo the busulfan test dose as an outpatient, with inpatient admission on day -6.

Busulfan pharmacokinetic studies: Patients will receive a test dose of busulfan at 32mg/m² i.v. over on day – 7 for measurement of pharmacokinetics to determine the dose that will give a daily AUC of 4000 μ Mol-min \pm 12% on days –5 through day –2. Blood samples (5ml each) will be drawn on day –7 at 30 min after the start of infusion and 5 min. before the end of infusion, then after the end of infusion at 15, 30, 60 min. and at 2, 4, 6 and 8 hours, and one sample approximately 10-11 hours.

Pharmacokinetic analysis and individualized IV busulfan dose will be calculated and ordered on day –6. Follow-up PK samples (quality control) will be drawn on days –5 and if necessary, for fine-tuning of the busulfan dose, and if necessary on day –3. Patients receiving the fixed-dose treatment arm will also have PK studies performed on day(s) –5, and if necessary on day –3 to allow for monitoring and if necessary, adjustment of busulfan dosing per above. This complete sampling schedule will be replaced with a limited sampling schedule when a validated limited sampling assay becomes available.

5.2 Allogeneic Stem Cell Collection

Stem cells will be harvested following MDACC Apheresis Unit or National Marrow Donor Program standard operating procedures. The choice between bone Marrow stem cells or blood stem cells will be made as per department of blood and marrow transplantation standard guidelines.

5.3 Post-transplant care

Post transplant care outlined below is considered standard clinical practice in BMT

GVHD prophylaxis: GVHD Prophylaxis will consist of tacrolimus and methotrexate, starting from day-2. Tacrolimus blood levels will be monitored and dose adjusted as clinically indicated. Patients will also receive methotrexate 5 mg/m² on days 1,3,6, and 11 post BMT.

Donor leucocyte infusion (DLI): Patients with evidence of residual disease or progressive disease but without GVHD one month after stopping immunosuppression, may receive DLI as per departmental guidelines for dose and schedule.

Supportive Care: G CSF, prophylactic antibiotics, antivirals, antifungal and therapeutic antibiotics, transfusions as clinical indicated by the patients condition, will follow BMT standard practice. Due to the possibility of drug interaction with busulfan, Tylenol is contraindicated from day –5 to day 0, and alternative medications should be used.

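### The acetaminophen restriction starts on day −5 and so misses the day −7 busulfan test dose that sets each patient's initial individualized dose

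*Combined protocol and SAP*

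**What the plan says.** The supportive-care paragraph of Section 5.3 gives both the reason and the window: "Due to the possibility of drug interaction with busulfan, Tylenol is contraindicated from day" −5 to day 0. Possible interaction with busulfan is the only reason given.

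Section 5.1 sets out when busulfan is given and how its dose is chosen:

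- "Treatment will start on D-7 as per the schema shown below". The schema puts the 32 mg/m² test dose on that day and the treatment doses on days −5, −4, −3 and −2.
- The test dose is "for measurement of pharmacokinetics to determine the dose that will give a daily AUC of 4000" µMol-min, ± 12%, on the four treatment days. Blood sampling runs to about 10–11 hours, and the individualized dose is calculated and ordered on day −6.
- "Patients may also undergo the busulfan test dose as an outpatient, with inpatient admission on day" −6.
- "Follow-up PK samples (quality control) will be drawn on days" −5 and, if necessary, −3, so that the dose can be fine-tuned.
- Some patients have no test dose: "If the patients cannot undergo the pharmacokinetic studies, the patient will not receive the 32 mg busulfan" test dose, and they start at 100 mg/m².

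**The concern.** A test dose predicts treatment exposure only if clearance is the same on the test day as on the treatment days. If acetaminophen alters busulfan clearance, the written window creates a mismatch between the two: the drug is not barred while clearance is measured, and it is barred while the resulting dose is given. The error would pass straight into the dose ordered on day −6.

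The outpatient option makes this more likely in practice, because a patient at home may take a common analgesic without being asked about it. The instruction also sits under post-transplant care, where staff arranging a day −7 visit may not look.

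At stake is the accuracy of the first one or two treatment doses, in patients who have the test dose. This is a gap in the window. The two sections do not contradict each other.

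**Working it through.** **Schedule check** (Sections 5.1 and 5.3)

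| Day | Busulfan event | Acetaminophen barred? |
|---|---|---|
| −7 | Test dose, sampling to about 10–11 h | No |
| −6 | Individualized dose calculated and ordered | No |
| −5 | Treatment dose 1, follow-up PK | Yes |
| −4 | Treatment dose 2 | Yes |
| −3 | Treatment dose 3, PK if necessary | Yes |
| −2 | Treatment dose 4 | Yes |
| −1, 0 | None | Yes |

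The window covers all four treatment doses and runs two days past the last one. It opens two days after the test dose and one day after the dose is ordered. No other section restricts acetaminophen on day −7 or −6.

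**Illustrative size.** The documents contain no figure to reproduce here, and they give no mechanism, direction or size for the interaction. The relative error e in test-dose clearance is therefore assumed, over a range of 10% to 30%.

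The dose is set as 4000 × measured clearance. If treatment-day clearance differs from the measured value, the delivered daily AUC is

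4000 × (measured clearance ÷ treatment-day clearance) = 4000 × (1 ± e).

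The target band is 4000 × 0.88 = 3520 to 4000 × 1.12 = 4480.

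The four-day target is 4 × 4000 = 16,000. With k uncorrected doses the total is k × 4000 × (1 ± e) + (4 − k) × 4000, a relative shift of ± k × e ÷ 4.

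| Assumed e | Daily AUC | Inside 3520–4480? | Four-day total, k = 1 | Four-day total, k = 2 |
|---|---|---|---|---|
| 10% | 3600 or 4400 | Yes | 15,600 or 16,400 (±2.5%) | 15,200 or 16,800 (±5%) |
| 15% | 3400 or 4600 | No | 15,400 or 16,600 (±3.75%) | 14,800 or 17,200 (±7.5%) |
| 20% | 3200 or 4800 | No | 15,200 or 16,800 (±5%) | 14,400 or 17,600 (±10%) |
| 30% | 2800 or 5200 | No | 14,800 or 17,200 (±7.5%) | 13,600 or 18,400 (±15%) |

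**Why k is 1 or 2.** The day −5 dose has been given by the time its own samples can be analysed, so at least one dose rests on the test-dose estimate. Section 5.1 does not state the turnaround for follow-up PK. If it matches that of the test dose (sampled one day, dose ordered the next), correction comes on day −4 at the earliest (k = 1), or on day −3 if it takes a day longer (k = 2).

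**The case against.** The case for leaving the text alone has five parts.

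1. **Purpose.** Section 5.3 does not mention clearance or dose-setting. The window fits the four full doses plus two days, so the aim may be to limit risk at full dose. Leaving out a single dose of about a third of the nominal 100 mg/m² could then be deliberate. Nothing in Section 5.3 supports that distinction: it cites interaction with busulfan in general, and the day −7 dose is busulfan. Even on that reading, the measurement would still be unprotected if clearance is what changes.
2. **Size.** Harm needs a real interaction, an effect on clearance, acetaminophen use around day −7, and an error above 12%. The documents establish none of these. This stands in full, and the table above is hypothetical.
3. **Built-in check.** PK on day −5, and on day −3 if needed, falls inside the restriction and would detect and correct a wrong estimate. This largely stands. It limits the problem to the first one or two doses but cannot correct a dose already given.
4. **Tolerated imprecision.** Patients who cannot have the PK studies start at a flat dose and are adjusted from day −5, so the plan already accepts a less exact start for some. This is fair as to seriousness. It is no reason to weaken a measurement made specifically to avoid that imprecision.
5. **Standard practice.** Supportive care follows departmental practice, which may already cover day −7. The documents do not say so, and the window that is written leaves that day out.

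**Conclusion.** The gap is real on the face of the text. The restriction exists because of busulfan, yet it omits the one busulfan dose given to set the others. Its importance is minor. The documents establish only that an interaction is possible. If acetaminophen around day −7 distorted measured clearance by 15% to 30%, the first daily AUC would fall outside the target band, and the four-day total would shift by ±3.75% to ±7.5% with one dose affected or by ±7.5% to ±15% with two. At 10%, the daily AUC stays inside the band. These figures rest on the assumed error, on doses being proportional to measured clearance, and on full correction once follow-up PK is available. Patients without a test dose are unaffected, and no effect on the non-relapse mortality stopping rule or the sample size is shown.

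**What to change.** For patients having the test dose, start the acetaminophen restriction no later than the day −7 test dose and continue it to day 0. The sponsor should decide whether a washout before day −7 is needed, since the documents give no basis for choosing one. State the restriction in the outpatient test-dose instructions, and record any acetaminophen use around day −7 so that affected PK results can be identified. Patients without a test dose keep the present window.

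Moving the start date is the essential change. The washout and the recording are useful additions. The cost is one revised sentence, one line of patient instruction and one concomitant-medication field, plus at least two more days without one analgesic for patients who have the test dose. Section 8.0 reports 49 of a planned 110 patients enrolled as of September 2011, so from that point at most 110 − 49 = 61 further patients could benefit, fewer if some have no test dose.

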6.0 Evaluation During Study

Evaluations for this study (6.1-6.5) are considered standard practice in BMT and should be done around 1, 3, 6, 9, 12, 18 and 24 months post transplantation. If clinically indicated these studies may be done at other time points to evaluate for potential relapse of the underlying malignancy, which can replace the nearest planned time points. After two years patient will be seen annually or information about patient's condition will be obtained by a telephone call or written communication.

- 6.1 Bone marrow Bx and aspirate with cytogenetics, and chimerism studies.
- 6.2 History and physical examination with evaluation of adverse events including GVHD
- 6.3 CBC, differential, platelets
- 6.4 SGPT, calcium, glucose, uric acid, magnesium, LFT, serum bilirubin, BUN and creatinine, serum protein, albumin, alkaline phosphatase, electrolytes.
- 6.5 Peripheral blood for chimerism studies.(the first chimerism study will be done 3-4 weeks post transplant).

7.0 Criteria for Study Evaluation

7.1 Primary end point:

Deaths not attributable to the disease recurrence will be considered as an event for assessment of non-relapse mortality.

7.2 Secondary end points:

Engraftment is defined as a sustained ANC $\geq 0.5 \times 10^9/L$ for 3 consecutive days and evidence of donor chimerism by D+28 (the first chimerism study will be done 3-4 weeks post transplant).

Primary Graft Failure is defined as failure to achieve an ANC $\geq 0.5 \times 10^9/L$ for 3 consecutive days by day 28, with <10% cellularity on bone marrow biopsy and no evidence of donor chimerism.

Secondary graft failure is defined as a sustained declined of ANC $<0.5 \times 10^9/L$ for 3 consecutive days after initial documented engraftment with no evidence of disease progression.

Complete remission is defined as per response criteria defined by European Myelofibrosis network. (appendix)

Relapse will be recorded by the day of detection.

Progression free survival is defined as the interval between day of transplant and day of death or disease progression.

Overall Survival is defined as the interval between day of transplant and day of death.

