8.0 Statistical Considerations

This is a phase II study with a primary objective of assessing the safety of Fludarabine, and Busulfan as preparative regimens for allogeneic stem cell transplantation in patients with Myelofibrosis and MDS. Patients enrolled in the study will be younger than 75 years of age and must have an HLA matched or at least a 9/10 antigen matched related or unrelated donor. The major reason for treatment failure in these patients is transplant related mortality. Therefore, in order to assess the primary objective of safety, the primary outcome measure will be the rate of non-relapse mortality (NRM) at 100 days. We will define non-relapse mortality as any death not attributable to disease recurrence. The cumulative incidence rates of NRM ranged from 27%-48% in three studies of younger patients with this disease. The NRM rate is expected to be much higher in this mostly older group of patients with advance myelofibrosis we are proposing to treat because NRM increases with age and coexisting medical illnesses. Therefore, the goal of the trial is to achieve better than a 30% NRM rate at 100 days post transplant with this treatment regimen. The proposed trial will evaluate the role of allogeneic stem cell transplantation a using reduced-intensity conditioning regimen of fludarabine and busulfan. These patients will receive 4 days of the Fludarabine regimen and 2 days of the Busulfan regimen. The maximum total sample size for this trial was originally 30 patients. It was increased in July 2009 to 60 patients. As of September 2011, 49 patients have been enrolled, and we now plan to increase enrollment to 110 patients. We expect to accrue 20 patients a year for a total of 3 years. The goal of the trial is to achieve better than a 30% NRM rate at 100 days post transplant. We will stop the trial if we have evidence that the NRM rate is higher than targeted.

The method of Thall and Simon will be employed to perform interim safety monitoring. As of September 2011, a total of 49 patients have been enrolled, of which 45 have been evaluated for NRM at day 100. Monitoring has proceeded according to the original stopping rule with no need for early study termination. For the remaining 65 patients, we will employ the following monitoring rule. The trial will be stopped early if:

$$\Pr[\theta \in E, D > 0.30 | \text{data}] > 0.90$$

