Efficacy endpoints such as time to engraftment, complete remission (CR), progression-free survival (PFS), and overall survival (OS) will be evaluated after 3-years of follow-up. We will estimate each of these efficacy endpoints with the Kaplan-Meier estimators. In addition, we will report each of the estimates along with their corresponding two-sided 95% confidence intervals. We will use Cox proportional hazards regression analysis to assess the association between the above survival parameters and clinical and demographic covariates of interest. We will use logistic regression to assess the association between clinical response (CR/PR vs. SD/PD) and the same covariates.

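### Complete remission is defined for every patient by myelofibrosis criteria, although MDS without fibrosis is eligible and the CR and response analyses take no account of diagnosis

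*Combined protocol and SAP*

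**What the plan says.** All references are to the combined protocol and SAP.

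- **Eligibility (Section 3.0, first inclusion criterion).** After idiopathic myelofibrosis and myelofibrosis secondary to PV or ET, the list continues "or Myelodysplastic syndrome with or without fibrosis".
- **Population in the statistical section (Section 8.0).** The study is of "preparative regimens for allogeneic stem cell transplantation in patients with Myelofibrosis and MDS". The primary objective in Section 1.0 is narrower: "preparative regimen for allogeneic stem cell transplantation in patients with myelofibrosis as determined by non-relapse mortality".
- **CR as an endpoint (Section 1.0, item 1.2).** It is listed as "Complete clinical/hematological remission".
- **CR definition (Section 7.2).** "Complete remission is defined as per response criteria defined by European Myelofibrosis network", with a pointer to an appendix. No other response system is named.
- **Analysis (Section 8.0, Secondary Endpoints).** For CR, time to engraftment, PFS and OS: "We will estimate each of these efficacy endpoints with the Kaplan-Meier estimators", each with a two-sided 95% confidence interval. A logistic regression then contrasts CR or PR with SD or PD. Neither analysis is limited to one diagnosis or split by diagnosis.

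**The concern.** A response rate can be interpreted only if a responder means the same thing throughout its denominator. Here the denominator can hold two diseases, while the scoring system is named for one of them. This is more than a missing detail: the plan states a rule, and the rule covers patients for whom it was not named.

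The protocol's own background shows why the fit is doubtful. Section 2.2 treats marrow fibrosis as the defining feature of myelofibrosis. Section 2.3 describes benefit after transplant as fibrosis resolving, the spleen shrinking, transfusions no longer being needed and counts improving. A patient with MDS and no fibrosis has no fibrosis to resolve. Under a literal reading, such a patient might be scored a failure, might pass a fibrosis item without any change, or might be left to the assessor's judgement. The plan does not say which.

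Two results are at stake. The pooled CR rate would depend partly on the mix of diagnoses. In the regression, a covariate associated with diagnosis could appear to predict response only because the two diseases were scored on different footings.

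**Working it through.** **No stated figure to reproduce.** The documents give no CR rate, target, power or sample size based on CR. The check is therefore a comparison of the sections, followed by an illustration under stated assumptions.

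**Step 1: the sections side by side.**

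| Question | Where | Answer |
|---|---|---|
| Can a patient with MDS and no fibrosis enrol? | Section 3.0 | Yes |
| Does the statistical section count MDS in the population? | Section 8.0 | Yes |
| Which CR criteria apply to that patient? | Section 7.2 | European Myelofibrosis network; no alternative named |
| Are CR or the regression restricted or split by diagnosis? | Section 8.0 | No |

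The mismatch follows from these four answers and needs no outside source.

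**Step 2: how far could the pooled rate move?** Inputs:

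- N = 110, the planned maximum in Section 8.0.
- c, the CR rate among patients the criteria fit. Assumed; not in the documents.
- m, the share of patients the criteria do not fit. Assumed; not in the documents.

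If no affected patient can meet the criteria, the reported rate is c(1 − m). If every affected patient meets them, it is c(1 − m) + m. The gap between the bounds is m, whatever c is.

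For c = 60% and m = 20%, 22 patients are affected and 88 are not:

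- lower bound: 0.60 × 88 / 110 = 52.8 / 110 = 48%
- upper bound: (52.8 + 22) / 110 = 74.8 / 110 = 68%

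| m | Affected of 110 | Lower | Upper |
|---|---|---|---|
| 10% | 11 | 54% | 64% |
| 20% | 22 | 48% | 68% |
| 30% | 33 | 42% | 72% |

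With m = 20% and other assumed values of c, the bounds are 32% to 52% for c = 40%, and 64% to 84% for c = 80%.

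**Step 3: precision if CR is reported by diagnosis.** The half-width of a simple binomial 95% interval is 1.96 × √(c(1 − c)/n). With c = 60%, and all 22 of the other patients taken to have MDS:

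- all 110 patients: 1.96 × √(0.24/110) = 9.2 points
- 88 myelofibrosis patients: 1.96 × √(0.24/88) = 10.2 points
- 22 MDS patients, if their CR rate were also 60%: 1.96 × √(0.24/22) = 20.5 points

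At m = 20% the lower bound lies 60 − 48 = 12 points below the assumed rate. In that extreme case the shift would exceed the 9.2-point sampling half-width.

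**The case against.** **The criteria cannot be seen.** Section 7.2 sends the reader to an appendix that is not in the public text. It could contain an MDS provision, and item 1.2 of Section 1.0 words the endpoint as clinical and hematological remission, with no mention of fibrosis. This stands as a limit on certainty. It rules out saying that the criteria are proven invalid for MDS. It does not remove the point, because Section 7.2 attributes the criteria to the myelofibrosis network alone. If the appendix does cover MDS, Section 7.2 need only say so.

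**Not every MDS patient is affected in the same way.** A reader might infer that all MDS patients are mis-scored. The argument that there is no fibrosis to resolve applies only to MDS without fibrosis. For MDS with fibrosis, the most that can be said is that the plan does not state whether the myelofibrosis system is meant to be used.

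**The bounds are extreme and the share may be small.** The upper bound needs every affected patient to be scored CR, including any who die early; the lower needs criteria that none of them can meet. Most of the protocol describes a myelofibrosis trial, and no expected number of MDS patients is given. This stands: the range shows what is possible and is not an estimate.

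**The consequence can be overstated.** A reader might infer that comparison with the earlier transplant series is spoiled. No CR comparison is planned, and Table 1 reports non-relapse mortality and survival, not CR. CR also has no hypothesis, power or decision rule attached.

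**Analysts would use sensible MDS criteria anyway.** Perhaps, but the plan does not say so, and choosing the criteria once outcomes are known is the discretion that prespecification should remove.

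**Conclusion.** The concern holds as an inconsistency between Sections 3.0, 7.2 and 8.0 that is worth correcting. At least the MDS patients without fibrosis are to be scored for CR by criteria named for a different disease, and both response analyses pool them with the rest.

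The size cannot be determined from the documents. The 48% to 68% range rests on an assumed 60% CR rate, an assumed 20% affected share, and CR in the affected group set to none or all.

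The reach is limited to unpowered secondary response endpoints. A reader might infer that the trial's main safety conclusion is in doubt, but the documents do not support that. The 100-day non-relapse mortality endpoint and its stopping rule count deaths not attributable to recurrence, OS counts deaths, and none of them uses the CR definition. PFS is touched only in that Section 7.2 states no progression criteria for MDS.

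**What to change.** **Section 7.2.** Apply the European Myelofibrosis network criteria to patients with myelofibrosis. Name a standard MDS response definition, covering CR, PR, SD and PD, for patients with MDS. State which of the two systems applies to MDS with fibrosis.

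**Section 8.0.** Report the CR rate by diagnosis, with each denominator; a pooled figure can be kept as a secondary summary. For the response regression, choose one of two routes in advance:

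- restrict it to myelofibrosis patients; or
- score each group by its own criteria and include diagnosis as a covariate.

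Adding diagnosis as a covariate without changing the scoring would not be enough, because the outcome would still mean different things in the two groups. Separate models by disease group are not required and may not be estimable: at the illustrative 20% share, the MDS model would rest on 22 patients.

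**Cost.** A few sentences, with no change to sample size or monitoring. Marrow with cytogenetics and blood counts are already scheduled in Section 6.0 (items 6.1 and 6.3). Since 49 patients had been enrolled by September 2011, those already treated would need to be assigned to a system and scored by it, preferably before any CR results are tabulated. The price is precision: if 88 of 110 patients have myelofibrosis, their interval widens modestly, while an MDS-only rate would be imprecise and should be presented as descriptive.
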